4.3. Expected duration of the study

a. Time window of monitoring per patient:

Patients from each cohort will be studied during a total period of 4.5 hours, with repetitive blood sampling during 2 consecutive mornings from 10.45-13.00 h, after receiving an alternate injection of CRH or placebo each morning. To use the crossover design, the effects of the intervention during the first period (i.e. effect of CRH) must not carry over into the second period.¹⁶ Firstly, taking the half-life of hCRH (30.5 +/- 3.3 min) into account, the requirement for a wash-out of 5 times the drug half-life (152.5 min) is sufficient to meet this assumption.¹⁷ Secondly, based on the fact that the cortisol clearance is reduced with at least 50% in critical ill patients than in healthy individuals, it is justifiable to perform the second alternate injection on the morning after the first injection.¹

b. Calculated sample size:

Based on the available literature⁹, we calculated to require 20 patients per cohort in order to detect a potential Cushing-like suppression of the ACTH response to CRH in critically ill patients, in comparison with the response of 20 healthy volunteers, with an alpha error of 1% (to correct for the multiple comparisons of each of the 3 patient cohorts with the healthy controls) and >80% power. In more detail: we expect an effect size of 1.20 based on previous findings, reporting a difference of mean delta AUC ACTH of 2159 to 795 pmol L⁻¹ min, with a common standard deviation of 1136 pmol L⁻¹ min.⁹ Power calculation was performed with an independent T-test for comparison of 2 means, assuming equal variances.

To take into account a potential increase in variation due to the heterogenous critical illnesses, we will double the number of patients to 40 per cohort. With 40 patients per cohort, we can detect a reduction of 30% in the ACTH responses to CRH between 2 patient cohorts, with an alpha error of 5% and >80% power (power calculation was performed as explained above, based on a reduction of 30% of 2159 pmol L⁻¹ min with the same standard deviation⁹). Recruitment of patients will continue until the preset number of 40 patients is reached in the 3 patient cohorts, with equal proportions of ICU admission categories among the groups.

c. Study duration:

Based on a retrospective analysis of the mean stay of patients in the ICU, we estimate that the study will take approximately one year to finalize recruitment.

5. Study Procedures and sample collection

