5.1 Patients group

After informed consent, each patient from each cohort will be randomized for the order of CRH or placebo injection into two crossover study groups. Consecutive patients will be randomly assigned to 'first placebo' or 'first CRH' using blinded envelopes, stratified according to the 3 'time in ICU' cohorts. At 11.00 am, after 2 baseline blood samples (EDTA, 4ml) (-15 and 0 min), 100µg CRH or placebo (0.9% NaCl) will be injected as an intravenous bolus. Blood samples (EDTA, 4ml) will then be obtained at 5, 10, 15, 30, 45, 60, 90, and 120 minutes after injection to determine plasma ACTH and cortisol concentrations. The next day, each patient will receive the alternate injection, and the same blood sampling protocol as the day before (Figure 1). Since for each participant the measured effect is the difference between the response to the injection of CRH and placebo, variability is reduced.¹⁶

Injections of CRH or placebo will be given through a peripheral or central venous catheter, followed by a flush with ±5 ml (depending on the distance between the injection point and the insertion point of the catheter) of normal saline (NaCl 0.9%) to guarantee a full injection of the entire dose, and blood samples are drawn from an arterial or central venous catheter, all in situ and inserted for clinical purposes. The total amount of blood sampled per session is 40ml (Good Clinical Practice (GCP) consists of 40 ml per day). Some patients may experience mild, brief facial flushing immediately after injection, but at this dose level no other side effects have been reported.¹⁸ Allergic reactions have also not been reported.

[figure not shown]

Figure 1: Study protocol. Patients from the 3 cohorts will be randomized for the order of CRH or placebo injection into two crossover subgroups. Each patients from each subgroup will be studied during a total period of 4.5 hours, with repetitive blood sampling during 2 consecutive mornings from 10.45-13.00 a.m.

The ACTH and cortisol responses to CRH/placebo will be correlated with available demographic and clinical data.

Such stored patient data include:

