5.2 Control group

Time profiles of ACTH and cortisol response to exogenous CRH are not clearly defined in the literature. Especially data from healthy volunteers with a comparable age, gender and BMI as our patient population are lacking. To compare the evolution of the ACTH and cortisol response during critical illness with healthy reference values, we will use the same study protocol as for the patients in 20 demographically matched healthy volunteers, with repetitive blood sampling during 2 consecutive mornings from 10.45-13.00 h, after receiving an alternate injection of CRH or placebo each morning. Volunteers will be asked to limit their morning nutritional intake to a European breakfast.

6. Compensation for control group

Healthy control subjects will be compensated for all expenses made to participate in the study, such as transportation cost and costs for parking space, and will be offered a meal on each study day and an overnight stay in Leuven. Furthermore, a gift card (value card worth 50 EUR) will be offered as an additional reward.

7. Statistics

First, the response to CRH injection (changes over time in plasma ACTH and cortisol concentrations) will be corrected for its corresponding placebo test result (changes over time in plasma ACTH and cortisol concentrations), resulting in a delta AUC value. The delta AUC values will be compared between each of the 3 cohorts and the healthy reference group, with correction for multiple comparisons with use of ANOVA (Bonferroni correction of the alpha error to correct for the multiple comparisons of each of the 3 patient cohorts with the healthy controls), after transforming the data to normally distributed values if needed. If the latter is not possible, non-parametrical tests will be used.

Second, for those patients from whom multiple CRH test results were collected, changes in delta AUC values within these patients will be analyzed with use of mixed models / repeated measures ANOVA after transforming the data to normally distributed values if needed.

Third, correlations between the ACTH and cortisol responses to exogenous CRH and clinical risk and outcome parameters will be done with the use of Pearson tests. Fourth, these measurements will be compared in patients with a favorable and a non-favorable clinical outcome.

8. Ethics and regulatory approvals

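### The primary ANOVA of delta AUC makes no use of the baseline samples drawn on both mornings as a covariate, which may cost precision but does not bias the result

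*Protocol*

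**What the plan says.** Section 5.1 (Patients group) gives the injection "after 2 baseline blood samples (EDTA, 4ml) (-15 and 0 min"), and the next day uses "the same blood sampling protocol as the day before". Section 5.2 applies the same study protocol to the controls. Every participant is therefore due to have a measured starting level of ACTH and cortisol on the CRH morning and on the placebo morning.

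Section 7 (Statistics) reduces each participant to a single number per hormone: "First, the response to CRH injection (changes over time in plasma ACTH and cortisol concentrations) will be corrected for its corresponding placebo test result". It then says: "The delta AUC values will be compared between each of the 3 cohorts and the healthy reference group". The test is an ANOVA with Bonferroni correction, after transformation if needed, with a non-parametric fallback. No covariate is named. The text does not say whether the AUC is total or measured above that morning's baseline.

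Section 5.1 credits the within-person difference with a gain in precision: "Since for each participant the measured effect is the difference between the response to the injection of CRH and placebo, variability is reduced". The power calculation in section 4.3 b is an unadjusted two-sample t-test.

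**The concern.** Subtracting the placebo-day response removes a participant's stable hormone level. It does not remove a chance difference in starting level between the two mornings. Section 2 describes ACTH and cortisol secretion as pulsatile (from nocturnal data), and ICU patients can change from one day to the next, so such differences are plausible.

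How they enter the outcome depends on the AUC definition:

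- **Total AUC.** The part of the starting difference that persists through the test goes into delta AUC, multiplied by up to 120 minutes, and stays in the error term.
- **AUC above baseline.** The starting difference is subtracted as if it persisted unchanged for the full 120 minutes (slope 1). If it fades sooner, this over-corrects, and the sampling noise of the two baseline values is multiplied by 120 minutes and added.

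A regression on the baseline difference estimates the slope instead of fixing it at 0 or 1. At stake is precision for both hormones, obtainable from samples that are already planned.

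**Working it through.** **Inputs from section 4.3 b.** Mean delta AUC for ACTH 2159 vs 795; SD 1136; 20 controls; 40 patients per cohort; alpha 1% for cohort vs controls and 5% for cohort vs cohort. Sidedness is not stated. **Assumed, because the Protocol gives no value:** rho, the within-group correlation of delta AUC with the baseline difference.

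**1. The plan's own figures (noncentral t).**
- Cohort vs controls: d = (2159 − 795)/1136 = 1.20, as stated ("we expect an effect size of 1.20 based on previous findings"). With 20 vs 20 and two-sided alpha 0.01, power is 85%, so the claim of more than 80% reproduces.
- Cohort vs cohort: 0.30 × 2159 = 648; d = 648/1136 = 0.570. The standard error is 1136 × √(2/40) = 254, giving a noncentrality of 648/254 = 2.55. Power is 71.2% two-sided and 81.1% one-sided, so more than 80% reproduces only one-sided. That is a separate matter from the covariate; 71.2% serves here only as the unadjusted starting point.

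**2. Effect of the covariate.** Residual SD = 1136 × √(1 − rho²).

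| Assumed rho | Variance removed | Residual SD | Power, 40 vs 40, 30% reduction, two-sided 5% |
|---|---|---|---|
| 0 | 0% | 1136 | 71.2% |
| 0.2 | 4% | 1113 | 72.9% |
| 0.3 | 9% | 1084 | 75.2% |
| 0.4 | 16% | 1041 | 78.5% |
| 0.5 | 25% | 984 | 82.8% |
| 0.6 | 36% | 909 | 88.3% |

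A gain of 5 points needs rho of about 0.33.

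**3. Cohort vs controls (40 vs 20, d = 1.20).** At alpha 0.05/3, power is 97.0% unadjusted and 99.4% at rho 0.5. At alpha 0.01 it is 95.4% and 99.0%. There is little to gain. If patient heterogeneity doubled the variance (an assumption; SD × √2), power at alpha 0.05/3 would be 73.5% unadjusted and about 86% at rho 0.5.

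**4. Dependence on the AUC definition.** Let s be the true slope, so that a baseline difference x adds s × 120 × x to total delta AUC. If total AUC has correlation rho with x, the variance of AUC above baseline, relative to total AUC, is (1 − rho²) + rho² × ((1 − s)/s)². With rho = 0.5:
- s = 0.5: 0.75 + 0.25 × 1 = 1.00
- s = 0.7: 0.75 + 0.25 × 0.184 = 0.80
- s = 1: 0.75 + 0 = 0.75

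The adjusted model has 0.75 in every case. Simulated power (6,000 runs, cohort vs cohort as in step 1) agrees:

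| True slope | Total AUC | AUC above baseline | Adjusted |
|---|---|---|---|
| 0.5 | 71% | 72% | 83% |
| 0.7 | 72% | 81% | 83% |
| 1 | 71% | 82% | 82% |

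A second simulation on the Protocol's sampling times, under assumed noise models, gave correlations with the baseline difference of 0.26 to 0.97 for total AUC and −0.18 to −0.79 for AUC above baseline. The adjusted model had the smallest SD in every scenario. Its advantage over AUC above baseline was negligible (39.9 vs 40.5) when the day shift persisted fully with little noise, and clear when the shift faded (for example 108.7 vs 131.3).

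**5. Is the covariate legitimate?** Each baseline precedes that morning's injection, and the order of CRH and placebo is randomised. Absent carry-over, the CRH-day minus placebo-day difference has expectation zero in every group, so adjusting for it does not remove the group differences in basal ACTH or cortisol that the trial studies. Adjusting for the absolute level could remove them.

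**The case against.** The strongest reply is that nothing here is an error. An ANOVA of a placebo-corrected AUC is valid and unbiased, and covariates and the AUC formula may be settled in a SAP that is not shown. That stands as a limit on weight: the point concerns the efficiency of an analysis that the Protocol does name.

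A reader might infer that morning-to-morning shifts certainly remain in the error term. The Protocol does not support that. Its description, "the response to CRH injection (changes over time in plasma ACTH and cortisol concentrations) will be corrected for its corresponding placebo test result", can be read as change from baseline, in which case the shift is already subtracted and only the fixed slope and the baseline noise remain.

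A reader might also infer that the number of 40 per cohort rests on the between-cohort contrast. Section 4.3 b instead doubles 20 to 40 to allow for heterogeneity among patients, and gives the 30% figure as what 40 can then detect. The contrasts spelled out in section 7 are cohort versus controls, where power is ample at the stated SD. The between-cohort contrast still matters, because section 3.1 makes comparison across increasing duration of illness the primary objective.

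The SD of 1136 comes from a cited study, and the Protocol does not say how baseline was handled there. If it was already baseline-corrected, the gains over total AUC do not apply to it.

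Finally, a pooled slope can lose precision if slopes differ greatly between groups. Suppose slope 1 in 120 patients, slope 0 in 20 controls, and equal covariate variance. The pooled slope is 120/140 = 0.857. The covariate's share of the variance of a cohort–control contrast is 1/40 = 0.025 unadjusted, and 0.143²/40 + 0.857²/20 = 0.037 adjusted. At a control slope of 0.3 the pooled slope is 0.9 and the order reverses: 1/40 + 0.3²/20 = 0.030 unadjusted against 0.1²/40 + 0.6²/20 = 0.018 adjusted. This calls for a slope check; it is not a reason to leave the covariate out.

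**Conclusion.** The point holds as a possible loss of efficiency. The Protocol collects a useful covariate on both mornings, and its named primary analysis does not use it.

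The size cannot be fixed from the Protocol. On its inputs and an assumed rho of 0.3 to 0.5, power for the 30% between-cohort contrast goes from 71% to between 75% and 83%. The gain is about 2 points or less when rho is 0.2 or below, small for cohort versus controls at the stated SD, and nil over AUC above baseline when the true slope is 1. These figures assume a two-sided test, a common slope, and no carry-over into the second morning's baseline.

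Two stronger conclusions might be drawn, and neither is supported. The result is not biased by omitting the covariate. And the gap between 71% and the stated power of more than 80% does not come from the missing covariate: it arises from reading the 5% test as two-sided.

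**What to change.** In section 7, before any data are seen:

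- Make the primary model a linear model of delta AUC on group plus the within-person baseline difference: the mean of the −15 and 0 min samples on the CRH day minus the same mean on the placebo day. Fit it separately for ACTH and cortisol, with the planned Bonferroni contrasts.
- State that the absolute baseline level is not a covariate.
- Allow a separate slope for controls, with the contrast read at a baseline difference of zero, or check that slopes are homogeneous.
- If data are transformed, compute both outcome and covariate from concentrations on the same scale. Differences can be negative, so they cannot simply be logged.
- Say whether AUC is total or above baseline. On the untransformed scale, with the same two-sample baseline mean, net area and a common slope, the adjusted contrasts are then the same under either definition.
- Keep the unadjusted ANOVA, or the planned non-parametric test, as a sensitivity analysis.

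Cost: a few sentences and one or two degrees of freedom, with no new patients or samples. A rule is needed for missing baseline values. The model relies on no carry-over into the day-2 baseline, and if rho is near zero it gains nothing.

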APPENDIX 1:

1. Informed Consent form for the patient - Versie 1.2
2. Informed Consent form for the legal representative of the patient - Versie 1.2
3. Opting out form for the patient - Versie 1.2
4. Informed Consent form for the healthy volunteer - Versie 1.2

1. Study Synopsis

Title of clinical study	The Dynamics of the ACTH and cortisol response to CRH stimulation during critical illness: A Randomized, double-blind, placebo-controlled crossover study
Protocol Short Title/Acronym	DACAR
Sponsor name	UZ Leuven
Principal Investigator	[name]. [name]
Medical condition or disease under investigation	Critically ill patients
Purpose of clinical study	To elucidate the central cause of the low circulating ACTH concentrations in the face of elevated circulating cortisol during acute, intermediate and prolonged critical illness
Primary objective	To document the ACTH and cortisol responses to exogenous CRH in patients with acute and prolonged critical illness
Secondary objective(s)	To describe the clinical causes/consequences of these changes
Study Design	Randomized, double-blind, placebo-controlled crossover study
Primary endpoints	The responses of plasma ACTH and cortisol to CRH and the changes hereof over time in ICU in relation to patient characteristics and outcome parameters
Sample Size	At least 120 patients - patient recruitment will continue until preset sample numbers are reached in 3 time-in-ICU-cohorts (40 patients per cohort) with a comparable distribution of ICU admission categories – and 20 healthy volunteers (controls who never stayed in the ICU)
Summary of eligibility criteria	Critically ill patients in the acute phase (ICU day 3-6), the intermediate phase (ICU day 7-16) and prolonged phase (ICU day 17-28) of critical illness
Maximum duration of treatment of a Subject	Not applicable
Version and date of final protocol	1.3; 05-07-2016
Version and date of protocol amendments	-

2. Background and rationale

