3.1 Study objectives

Our *primary objective* is to compare the ACTH and cortisol responses to exogenous CRH in patients with increasing duration of critical illness. Therefore we will investigate 3 cohorts of critically ill patients, matched for baseline characteristics (equal proportions of primary diagnostic category on ICU admission), during the acute, the intermediate and the prolonged phase of critical illness and compare these with a matched healthy control group. Cortisol binding proteins will also be assessed to calculate free cortisol. This will allow us to gain further insights in the potential (loss of) suppression of the central HPA axis in response to critical illness as well as any eventual evolution to (absolute) adrenal failure. To further reduce the impact of confounding covariates, each patient will serve as his or her own control in a crossover design. Our *secondary objective* is to describe the possible causes/consequences of such changes within the HPA-axis.

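### The between-cohort (illness-duration) part of the primary objective is powered in section 4.3 b at an unadjusted 5%, but section 7 neither lists that comparison nor covers it in its multiplicity correction

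*Protocol*

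**What the plan says.** **Objective and endpoint.** Under section 3.1 the primary objective "is to compare the ACTH and cortisol responses to exogenous CRH in patients with increasing duration of critical illness". The same paragraph adds that the investigators will "compare these with a matched healthy control group", so the objective has two parts. The synopsis gives as primary endpoint "The responses of plasma ACTH and cortisol to CRH and the changes hereof over time in ICU".

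**Sample size.** Section 4.3 b contains two power statements for the ACTH response. One is cohort against healthy controls, "with an alpha error of 1% (to correct for the multiple comparisons of each of the 3 patient cohorts with the healthy controls"). The other is between two patient cohorts: a 30% reduction, 40 per cohort, alpha 5%, power above 80%, by the same independent t-test. The second statement makes no adjustment for the number of cohort pairs.

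**Analysis.** Section 7 says: "The delta AUC values will be compared between each of the 3 cohorts and the healthy reference group". The method is ANOVA, with "Bonferroni correction of the alpha error to correct for the multiple comparisons of each of the 3 patient cohorts with the healthy controls". Its only analysis of time concerns patients tested more than once, and section 4.1 keeps those results out of the primary study.

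**The concern.** The three time-in-ICU cohorts exist so that responses can be compared by duration of illness. The objective asks for that comparison and the sample size is partly justified by it, yet the analysis section does not contain it. Two things follow.

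- An analyst who keeps to section 7 has only three comparisons with controls. A statement about duration would then have to rest on one cohort differing significantly from controls and another not, which is not a test of a difference between cohorts.
- An analyst who adds the cohort pairs at the 5% of section 4.3 b runs three further tests outside the stated correction. Which pairs to test, and how to adjust them, would be left open for a comparison that belongs to the primary objective.

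**Working it through.** **Inputs.** From section 4.3 b: "difference of mean delta AUC ACTH of 2159 to 795 pmol L⁻¹ min, with a common standard deviation of 1136 pmol L⁻¹ min"; 20 per group at 1% against controls; 40 per cohort at 5% between cohorts, for a reduction of 30% of 2159. Sidedness is not stated, so both are shown. Normal data and equal variances are assumed throughout.

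**1. The plan's own power figures.** The noncentrality is difference / (SD × √(2/n)), with the t distribution on 2n − 2 df.

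- Against controls: difference 2159 − 795 = 1364, effect size 1364/1136 = 1.20. Noncentrality = 1364 / (1136 × √(2/20)) = 3.80. Power at two-sided 1% is 85.4%. The claim of more than 80% is reproduced.
- Between cohorts: difference 0.30 × 2159 = 647.7, effect size 647.7/1136 = 0.570. Noncentrality = 647.7 / (1136 × √(2/40)) = 2.55. Power at 5% is 81.1% one-sided and 71.2% two-sided. The claim is reproduced only as a one-sided test; 80% two-sided needs 50 per cohort.

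**2. Which comparisons are covered where.**

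| Comparison | Objective (3.1) | Powered (4.3 b) | Tested in section 7 | In section 7's correction |
|---|---|---|---|---|
| Cohort vs controls (3 tests) | yes | yes, 1% | yes | yes |
| Cohort vs cohort (3 pairs) | yes | yes, 5% | no | no |

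**3. Family-wise error if the three pairs are run at 5% each.** For three independent tests it would be 1 − 0.95³ = 14.3%. The pairs share cohorts, and the studentized range for three groups of 40 (117 df) gives 12.2%. Adding the three control tests at 5%/3 (20 controls, simulation of 200,000 trials under the global null) gives 14.8%. The 5%/3 assumes a 5% family, because section 7 gives no figure. All of this is per hormone.

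**4. Reading duration from the control tests.** Trials of 40/40/40/20 were simulated with pooled variance (136 df) and the same true deficit from controls in all three cohorts, so that there is no duration effect. The table gives the share of trials in which at least one cohort is significant against controls and at least one is not.

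| True deficit (SD) | Tests at 5%/3 | Tests at 1% |
|---|---|---|
| 0.6 | 39% | 36% |
| 0.8 | 35% | 38% |
| 1.0 | 18% | 22% |
| 1.2 (planning value) | 5% | 8% |

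**5. The F gate.** With three groups, if any two of the pairwise nulls are true then the third is true as well. Either all three are true, and the overall F-test at 5% controls the error, or at most one is true, and a single 5% test controls it. Pairwise contrasts at an unadjusted 5% are therefore allowed once F is significant; simulated between-cohort error is 5.0%. At 40 per cohort, power for the acute-versus-prolonged contrast with a 0.57 SD difference is about 66% if the intermediate cohort equals one of the others, and about 59–60% if it lies midway. By comparison, Bonferroni over three pairs gives 54.3% two-sided and needs 66 per cohort for 80%.

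**The case against.** The strongest reply is that the between-cohort comparison is not undefined: section 4.3 b gives it a test, an alpha, an effect, an SD and a sample size. That stands. A reader might infer that the duration question has no alpha at all, and the document does not support this. What is missing is the step from section 4.3 b into section 7 and its correction.

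Secondly, comparison with controls is also part of the primary objective and has a test, a threshold and reproducible power. The synopsis even words the primary objective only as documenting responses. So it would be too strong to say that the trial cannot answer its primary question; the gap concerns the duration part.

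Thirdly, the protocol nowhere proposes to infer duration from significant and non-significant control tests, and at its planning effect the patterns disagree in only 5–8% of trials. This is fair. The simulation shows why section 7's tests cannot stand in for the missing one, especially for smaller deficits; it does not describe a planned analysis.

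Fourthly, ANOVA may imply an overall F-test, and a SAP may supply detail. But section 7 ties its correction to the control comparisons, and a four-group F that includes controls would not isolate duration. The mismatch lies between sections of the protocol itself.

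**Conclusion.** The point holds for the duration part of the primary objective. Section 3.1 asks for it and section 4.3 b powers it, but section 7 neither lists it nor corrects for it. If the three pairs are run as section 4.3 b implies, family-wise error is about 12% per hormone, or about 15% with the control tests at 5%/3. These figures assume normal data, equal variances, cohorts of 40 and 20 controls.

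Two further readings are tempting and not supported:

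- That sections 4.3 b and 7 use conflicting thresholds (1% against 1.67%). Section 7 states no number; 1.67% follows only if a 5% family is assumed. The stated 1% is stricter than 5%/3.
- That two hormones turn three control tests into six and break the error control. At the stated 1%, the error over all six tests is about 4.8%, so no excess arises.

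**What to change.** In section 7, add the between-cohort comparison of delta AUC as a primary analysis: an overall F-test across the three patient cohorts at two-sided 5%, followed by the three pairwise contrasts at 5% each only if F is significant. Label it as a family separate from the cohort-versus-control tests, and write into section 7 that those stay at the 1% already given in section 4.3 b. Cortisol can keep its place among the primary endpoints; this change does not require demoting it.

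In section 4.3 b, state the sidedness and restate the between-cohort power for the 30% reduction with 40 per cohort: 71% for a single two-sided 5% t-test (81% only if one-sided), and about 60–66% with the F gate.

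The cost is text only, with no new data, but there are two downsides to state openly. The two families are not jointly held at 5%: per hormone the bound is 5% + 3 × 1% = 8%. And power above 80% for the between-cohort comparison can no longer be claimed at 40 per cohort; even one two-sided t-test would need 50.

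### ACTH and cortisol are both primary, but the Bonferroni rule in section 7 counts three tests where there are six, and section 4.3b uses a different level for the same three comparisons

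*Protocol*

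**What the plan says.** The synopsis of the Protocol gives the primary endpoint as "The responses of plasma ACTH and cortisol to CRH and the changes hereof over time in ICU", and then adds the relation to patient characteristics and outcome. Section 3.1 states that the primary objective is to "compare the ACTH and cortisol responses to exogenous CRH in patients with increasing duration of critical illness", and adds a comparison with matched healthy controls. Neither place orders the two hormones or divides alpha between them.

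Section 7 compares the placebo-corrected delta AUC of each cohort with the healthy group, using ANOVA with a "Bonferroni correction of the alpha error to correct for the multiple comparisons of each of the 3 patient cohorts with the healthy controls". It gives no numerical level, does not mention the two hormones as a source of multiplicity, and lists no test of one cohort against another.

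Section 4.3b bases the sample size on ACTH alone, "with an alpha error of 1% (to correct for the multiple comparisons of each of the 3 patient cohorts with the healthy controls". It then doubles the cohorts to 40 and states a detectable 30% reduction "between 2 patient cohorts, with an alpha error of 5% and >80% power".

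**The concern.** The protocol commits itself to a correction, a count and a level, and these do not fit together. The count leaves out one of the two primary hormones. The sample size section gives the same reason for its correction as section 7, but uses a level that Bonferroni over three tests does not produce. The comparison by duration of illness, which is the core of the primary objective, is powered in 4.3b but has no place in the section 7 correction.

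At stake is which results may be called confirmatory. As written, a positive result for either hormone in any cohort could be reported as the primary finding, at a per-test level that depends on which section is followed. Only ACTH has a sample-size basis.

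**Working it through.** **Inputs from the Protocol.** Section 4.3b: mean delta AUC ACTH 2159 and 795, common SD 1136, alpha 1%, 20 vs 20, later 40 per cohort; 30% reduction, alpha 5%. Section 7: Bonferroni over three comparisons.

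**Assumptions.** Overall level 5%, since section 7 gives none. Correlation between the two hormones' delta AUC 0 to 0.9, since the Protocol gives none. Tests two-sided, since sidedness is not stated. No overall F-test is required before the contrasts.

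**The plan's own figure.** Effect size = (2159 − 795)/1136 = 1364/1136 = 1.20. A two-sided t-test at 1% with 20 vs 20 has power 85.4%, so the stated power above 80% is reproduced.

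**Per-test level.** Bonferroni over three at 5% is 0.05/3 = 1.67%. Three tests at 1% spend at most 3 × 1% = 3%. The 1% in 4.3b is therefore stricter than the rule in section 7.

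**Family-wise error, cohort vs control.** The bound is the number of tests times alpha. With independent tests the error is 1 − (1 − alpha)^k. The tests are not independent: the three contrasts share 20 controls, so any two of them correlate at (1/20)/(1/40 + 1/20) = 0.67. The simulated figures (400,000 runs, normal data, no true differences, 20/40/40/40) take this into account.

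| Tests | Alpha per test | Bound | If independent | Simulated |
|---|---|---|---|---|
| 3 (one hormone) | 1.67% | 5.0% | 4.9% | about 4.0% |
| 3 (one hormone) | 1% | 3.0% | 3.0% | about 2.5% |
| 6 (both hormones) | 1.67% | 10.0% | 9.6% | 5.8–7.9% |
| 6 (both hormones) | 1% | 6.0% | 5.9% | 3.7–4.9% |
| 6 (both hormones) | 0.83% | 5.0% | 4.9% | 3.1–4.1% |

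In the six-test rows the lower simulated figure belongs to correlation 0.9 and the higher to correlation 0.

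**Cohort vs cohort.** Three cohorts give three pairs. If all three ACTH pairs were tested at 5%, the simulated family-wise error would be 12.2%.

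**Power at the corrected levels, two-sided.** For cohort vs control at 40 vs 20 and effect size 1.20: 97.0% at 1.67%, 95.4% at 1%, 94.7% at 0.83%. For cohort vs cohort at 40 vs 40, the 30% reduction is 0.30 × 2159 = 647.7, and 647.7/1136 = 0.57. Power is then 71.2% at 5% and 54.3% at 1.67%. The stated power above 80% is met only by a one-sided test at 5% (81.1%).

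**The case against.** The strongest defence is that the protocol delivers what it says. It claims correction for three cohort-vs-control comparisons, and within each hormone the error is about 4.0% at 1.67% and 2.5% at 1%. It makes no claim across hormones. The aims are partly descriptive, the two hormones speak to different levels of the axis (pituitary and adrenal), and the handling of several endpoints is often left to a statistical analysis plan. This stands in part. A plan that makes two hormones primary need not treat them as one family, but it should say so, and here the protocol has itself fixed a count that ignores the second hormone.

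Three stronger readings are tempting, and the document does not support them.

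- A reader might infer that the family-wise error exceeds 5% whatever is done. At 1%, the only level printed for the control comparisons, all six tests stay at 3.7–4.9%.
- A reader might see the 1% and 5% in 4.3b as contradicting each other. They belong to different comparisons. The mismatch is between 1% and the 1.67% that section 7 implies, and it is on the conservative side.
- A reader might quote the 12% as the error of the planned analysis. Section 7 lists no pairwise cohort tests. The figure shows only what would follow if all three ACTH pairs were tested at the level used in 4.3b.

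The synopsis clause that ties the primary endpoint to patient characteristics is a loose phrase and not a further family of primary tests. The same synopsis makes clinical causes and consequences secondary, section 3.1 says that the secondary objective "is to describe the possible causes/consequences of such changes within the HPA-axis", and section 7 places correlations and outcome groups third and fourth.

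**Conclusion.** The point holds in a limited form. Applied as section 7 describes it, with 5% overall, the Bonferroni rule leaves a family-wise error of about 6–8% over the six primary control comparisons, a moderate excess. Sections 4.3b and 7 do not give the same level for the same three comparisons. The cohort-vs-cohort contrast belongs to the primary objective and is powered in 4.3b, but has no defined place in the analysis.

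The size rests on the assumed 5% overall level, on a hormone correlation between 0 and 0.9, and on treating the two hormones as one family because both are named primary without order. If the 1% of 4.3b is also meant for the analysis, the six control comparisons are already controlled, and what remains is to say so and to settle the cohort contrasts.

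**What to change.** State one alpha rule and use it in both 4.3b and section 7. Either of two forms would do.

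1. Keep both hormones primary and apply Bonferroni or Holm over all six cohort-vs-control tests. Bonferroni gives 0.05/6 = 0.83% per test. For effect size 1.20 at 40 vs 20, power falls from 97.0% at 1.67% to 94.7%.
2. Name delta AUC ACTH, the only endpoint with a sample-size basis, as the single primary endpoint, with Holm or Dunnett over its three control contrasts. Make cortisol a key secondary endpoint with its own three-test correction. The 5% then applies to each hormone separately and not to both together.

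Under the second form cortisol should not be made conditional on a significant ACTH contrast. The background is built on dissociation of the two hormones, and section 3.1 asks about adrenal failure, so an altered cortisol response with an unaltered ACTH response would be a result of interest.

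Label the cohort-vs-cohort contrasts secondary or exploratory, or include them in the correction and restate the power in 4.3b together with the sidedness of the test (two-sided 71% at 5%, 54% at 1.67%). As a minor tidy-up, move the clause on patient characteristics and outcome from the primary to the secondary endpoints in the synopsis.

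If the cohort contrasts stay exploratory, the change is to wording only. The price is a slightly stricter level per test in the first form, or cortisol no longer being primary in the second. If the cohort contrasts are made confirmatory, the loss of power is real and would have to be accepted or met with larger cohorts (66 per cohort for 80% two-sided power at 1.67%).
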